Exercise training: The 16-week Aim 1 exercise training period will begin within two weeks after the Pretest. Training sessions will be performed at one of the Wellness Centers described in Facilities, with potential for additional sites depending on needs and the availability of appropriate supervision. All participants already have free membership to the Wellness Centers as a benefit provided to Certificate Degree of Indian Blood (CDIB) cardholders. Free transportation will be arranged through a shuttle service already in place for medical visits. Fitness professionals at each center will provide instruction, supervision, and ongoing guidance to assure that exercise sessions are completed safely and effectively. Participants and their parent/guardian will be instructed that the exercise goal throughout the entire 48-week study is to achieve 60 min/day of moderateto-vigorous physical activity (MVPA), consistent with current guidelines for children (13, 31, 90). MVPA is defined as continuous exercise that elicits a heart rate \geq 70% of peak heart rate. Each participant will be able to choose the frequency of visits to the wellness center and the length of time engaged in MVPA, since the purpose of the study is to test the effect of incentives on exercise behavior. Several types of exercise can be selected, including walking, running, cycling, stair stepping, aerobic dance or other activities. Instructors will advise a gradual increase in exercise intensity and duration as tolerated over the first 2-3 weeks to allow for familiarization and safety. To promote healthy behavior within the community and foster social support, all participants will be invited to exercise with family members or friends if they choose and this will be recorded as a covariate. As in our previous studies, exercise intensity will be monitored by recording heart rate with a chest strap transmitter that outputs to a computer for quantification and data storage. These data will be used to document training sessions. To provide backup in the event of technical failure, training sessions will also be recorded in an exercise log by each participant and confirmed by fitness center staff. Exercise will be quantified by frequency (sessions per week), duration (length of sessions), and total volume (Metabolic Equivalent of Task-hours, MET-h, a measure of intensity relative to resting x activity time).

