After completing Aim 1 and the associated post-test, all participants who completed an average of \geq 1 exercise session per week will be eligible to continue on to Aim 2. The only difference between Aims 1 and 2 will be the financial incentive scheme; the overall exercise goals, and provision of transportation and professional oversight will remain the same. Similarly, after completing Aim 2 and the associated post-test, all participants who have averaged \geq 1 exercise session per week in Aim 2 will be eligible to continue on to Aim 3. No changes will be made to the exercise goals or availability of transportation and facilities in Aim 3.

To allow for potential schedule conflicts and missed sessions (e.g., illness, travel) participants will be allowed to "catch-up" by performing up to 3 extra sessions within the 3 weeks following a week with less than 3 sessions. Thus, if an entire week is missed due to illness, 12 sessions for payment can be completed over the next 3 weeks instead of the targeted 9 sessions. Additionally, participants will not be discouraged from performing more than the targeted exercise volume of 3 days per week of 60 minutes per session. Exercise beyond this target that is performed at school, at home or at the Wellness Centers is acceptable, since the goal of this program is to foster increased physical activity. Participants will be instructed to include such extra physical activity in their exercise log book, though they will not receive payment for days or time beyond the structured incentive program. This information will be used as part of the data analysis plan if applicable.

Post-training testing: After each of the 16-week exercise phases in Aims 1, 2, and 3, the clinical outcome tests performed at the baseline will be repeated. Staff that supervise exercise sessions will not be blinded to group assignment, but most other staff, including nurses and chemistry lab staff, will not know group assignments, so the potential for bias is expected to be low. The fasting blood sample will be acquired 2 days (38-48 hours) after the last exercise session in order to assess exercise adaptations that are distinct from the residual effects of the most recent training session. The exercise fitness and body composition tests will also be repeated at the end of each study phase.

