Group assignment: Within each Aim, participants will be assigned to one of two groups using a randomized stratified block design that was selected to reduce the potential for baseline variability among the groups. Participants will be assigned to blocks of 2 (duos) matched for age and sex. A participant who is not yet matched on the two factors will determine the age and sex for a newly established duo. The next participant to meet those matching criteria will be assigned to that duo. Each duo will have one participant in each of the intervention groups, but the group to which each participant in a block is assigned will be pre-determined by a unique random permutation.

Incentive programs

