Aim 1: This aim will test the hypothesis that the frequency of exercise sessions at the wellness center will vary with the amount of money offered for the number of sessions per week. Participants will be assigned to one of two groups that only differ in the payments for completing their exercise sessions. For both groups, payment will be provided for the number of sessions performed, up to 3 per week. As shown in Fig 2, the Control group can earn up to \$12 per week at a flat rate of \$4 per session, while those in the Incentive group can earn up to \$30 per week through an incentive structure meant to encourage exercise on 3 days per week. Qualifying exercise sessions for both groups must be \geq 20 minutes/session of MVPA during the first 3 weeks, increasing to \geq 30 minutes/ session of MVPA in weeks 4-16. To allow for rest breaks, the activity time can be accumulated rather than continuous. The plan for recording sessions and making up missed sessions is outlined in the Exercise Training section. By completing all of the targeted 48 exercise sessions participants can earn

Aim 1 payments, exercise sessions/week:									
Session of the week									
Group	Day 1	Day 2	Day 3	Max.					
Control	\$4	\$4	\$4	\$12					
Incentive	\$4	\$10	\$16	\$30					
Ai m 2 payments, exercise time/session: Time per session									
Group	20 min	40 min	60 mii	n Max.					
Control	\$4	\$4	\$4	4 \$12					
Incentive	\$4	\$7	\$10	0 \$30					
Fig 2. Aims 1 & 2 incentive structures. Values are payments per visit and weekly maximum.									

a maximum of \$192 (Control) or \$480 (Incentive) for exercise in this Aim.

Aim 2: This aim will test the hypothesis that exercise time per visit will vary with the amount of money offered for the length of exercise sessions. In this aim, as in Aim 1, the Control group will earn \$4 per session for up to 3 sessions per week. The Incentive group can earn up to \$30/week, with a payment structure based on the length of time for each exercise session (**Fig 2**). The incentive is meant to encourage at least 60 minutes of MVPA per exercise session, consistent with the daily activity recommendations for youth. As in Aim 1, this study phase is 16 weeks so completion of all 48 targeted exercise sessions will result in payments of \$192 (Control) or \$480 (Incentive).

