Data analyses: Since group assignments will be balanced for age and sex, the groups are expected to be similar at baseline. Additional comparisons will be performed to identify demographic or other variables on which the groups might differ (e.g., weight loss) that could affect the primary outcomes. Subsequent analyses will adjust for these potentially confounding variables. Regression models, which adjust for modifier (or confounding) variables identified in initial data exploration, will compare between-group differences in the primary outcomes. Since we anticipate that the number of fitness center visits, which is the primary outcome in Aim 1, will follow a Poisson distribution typical of counts, we will explore a multivariable Poisson regression model to analyze that aim. To assess Aim 2, a more conventional regression model will analyze the primary outcome, which is the total time that participants engage in exercise. The effects of exercise training on secondary outcomes will be analyzed similarly, using multiple linear regression. Analysis of Aim 3 will also utilize multivariate modeling to determine which factors, including exercise group assignment, best explain the change in exercise volume and clinical outcomes over the final phase of the study. Residuals generated from regression models will be inspected for normality and data will be log-transformed or subjected to nonparametric testing as appropriate. Aim 4 is a cross-sectional study design so the main effects of physical activity (high versus low), fitness (high versus low) and body size (normal weight versus overweight/obese) on biomarkers of metabolic disease risk will be initially determined using an analysis of variance approach, with Bonferroni tests to make pairwise comparisons between groups. A multivariate modeling approach, similar to that used in Aims 1-3, will be used to identify the best sets of predictor variables for specific biomarkers. A P value <0.05 will be considered statistically significant.

BIBLIOGRAPHY

- 2. Adams SH. Emerging perspectives on essential amino acid metabolism in obesity and the insulinresistant state. *Adv Nutr* 2: 445-456, 2011.

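### Aim 1's Poisson regression should name a standard-error method that uses the observed spread between participants, because visit-count variance may not equal the mean

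*Combined protocol and SAP*

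**What the plan says.** The Data analyses section makes the number of fitness center visits the Aim 1 primary outcome and anticipates that it "will follow a Poisson distribution typical of counts, we will explore a multivariable Poisson regression model to analyze that aim". It names no other model for this outcome. It does not say how standard errors will be computed, and it mentions neither a dispersion estimate nor a check that variance equals the mean.

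The one safeguard is general to all the regression models: "Residuals generated from regression models will be inspected for normality and data will be log-transformed or subjected to nonparametric testing as appropriate". The residual type, the form of inspection and the trigger for switching are not stated.

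Three design features bear on the spread of the counts:
- Under Exercise training, "Each participant will be able to choose the frequency of visits to the wellness center".
- Under Incentive programs, Aim 1, payment covers up to 3 sessions per week, with a target of 48 sessions over 16 weeks.
- That target is not a hard ceiling. Missed sessions can be made up, and "participants will not be discouraged from performing more than the targeted exercise volume of 3 days per week", although sessions beyond the paid scheme earn nothing.

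**The concern.** With model-based errors, a Poisson regression takes the width of its interval from the fitted mean. How much participants actually differ does not enter. Self-chosen attendance can make some participants regular and others rare visitors, which pushes variance above the mean. A limit on paid sessions can do the opposite if most participants settle near the target.

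In the first case the test of the incentive effect rejects too often at the stated P<0.05 and the interval is too narrow. In the second case it is conservative and loses power. The Aim 1 result would then rest on an assumed variance that the trial's own data could have replaced.

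**Working it through.** **No figure to reproduce.** The documents give no expected visit rate, SD, dispersion or power calculation for Aim 1.

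**Inputs from the documents.** 80-90 participants enter the exercise program (Design), allocated 1:1 in duos (Group assignment), so 40-45 per arm; 42 is used. Significance level 0.05 (Data analyses). Target 48 sessions (Aim 1).

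**Assumed inputs.** A two-sided test; model-based standard errors; mean visits of 16, 24 or 36; phi = variance/mean of 0.5, 2, 4 or 8, taken as what remains after covariate adjustment.

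**Step 1: the Poisson test alone.** With n per arm and common mean m, the model-based variance of the log rate ratio is 2/(nm). The true variance is 2·phi/(nm). Under no effect the Wald statistic therefore has standard deviation sqrt(phi), and n and m cancel:

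type I error = 2 × [1 − Φ(1.96/sqrt(phi))]

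| phi | 1.96/sqrt(phi) | type I error |
|---|---|---|
| 0.5 | 2.77 | 0.6% |
| 1 | 1.96 | 5.0% |
| 2 | 1.39 | 16.6% |
| 4 | 0.98 | 32.7% |
| 8 | 0.69 | 48.8% |

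Simulation at 42 per arm agrees. Negative binomial counts and beta-binomial counts on 0-48 give 16-17%, 32-34% and 47-49% at phi 2, 4 and 8. A common attendance probability of 0.5 on 0-48 has phi = 1 − 0.5 = 0.5 and gives 0.4-0.6%.

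For the interval, take m = 24. The model-based SE is sqrt(2/(42 × 24)) = 0.0445, so the limits are the estimate multiplied or divided by exp(1.96 × 0.0445) = 1.09. At phi 4 the SE should be 0.0891 and the factor exp(1.96 × 0.0891) = 1.19.

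**Step 2: covariates.** The planned model is multivariable, and covariates can absorb part of the spread. In simulations at mean 24 where they explain half of the between-person variance, residual phi is 1.49, 2.39 and 3.99 for total phi 2, 4 and 8, and the error is 11%, 21% and 35%.

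**Step 3: adding the fallback.** This needs an assumed rule, because the plan states none. Here a Shapiro-Wilk p<0.05 on Pearson residuals switches to a rank test; otherwise the Poisson result stands.

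| Attendance model | phi 2 | phi 4 | phi 8 |
|---|---|---|---|
| Negative binomial, mean 16 | 11.7% | 10.7% | 5.1% |
| Negative binomial, mean 24 | 13.7% | 15.0% | 7.4% |
| Negative binomial, mean 36 | 14.8% | 19.9% | 13.4% |
| Symmetric on 0-48, mean 24 | 15.8% | 28.3% | 8.6% |
| Skewed on 0-48, mean 36 | 5.7% | 4.3% | 5.1% |

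A separate run of the symmetric case at phi 4 gave 29%, with the check firing in only 15% of trials. Residuals can look normal while having four times the assumed variance.

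The result also depends on the rule. With uncapped counts at phi 4-8, Shapiro-Wilk on deviance residuals leaves 22-38%, whereas Kolmogorov-Smirnov against a standard normal leaves about 5%.

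**Step 4: the alternative.** With a t reference and no true effect, unadjusted runs over phi 0.25-8 gave 4.0-5.5% for Pearson-scaled errors and 3.5-5.6% for robust (HC1) errors. Adjusted runs gave 4.2-6.8% and 4.0-5.8%.

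**The case against.** The strongest reply is that Step 1 is not the procedure in the plan. Poisson regression is only to be explored, and a fallback follows. Where the fallback acts, it removes most of the inflation: at phi 8 the assumed rule leaves 5-13% in the Step 3 table, and it leaves 4-5% when attendance falls into two clusters. An analyst who looked at the residuals could also notice the problem. At phi 4, about 9-12 of 84 Pearson residuals exceed 3 in absolute value, and at phi 8 about 18-31 do. Phi 8 is itself an extreme shape on 0-48: at mean 36 it puts about 45% of participants at exactly 48 visits and 11% at 4 or fewer.

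All of this stands, and it limits the size of the point. It does not remove it, because protection then depends on the attendance shape and on choices the plan leaves open.

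Two stronger criticisms of the fallback might be inferred, or its opposite, and the documents support neither:
- That it yields no adjusted ratio. Log transformation is the option listed first. It allows an adjusted linear model with a ratio of geometric means, and it held about 4-5.6% when used throughout.
- That it can be trusted whenever attendance is skewed. Negative binomial counts are skewed too, and the assumed rule leaves 5-20% for them.

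**Conclusion.** The gap is real: the Aim 1 primary analysis assumes variance equal to the mean and prespecifies no variance method based on the observed spread. Conditional on model-based errors, an untriggered fallback and residual phi as stated, type I error is about 17%, 33% and 49% at phi 2, 4 and 8, and about 0.5% at phi 0.5. With one assumed form of the fallback it is about 14-29% for smooth heterogeneity at phi 2-4 (means 24 and 36; 11-12% at mean 16), about 5-14% at phi 8, and about 5% for bounded skewed attendance.

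A reader might infer that the trial runs a 17-49% false-positive risk, or that the counts are overdispersed. The documents establish neither. They give no dispersion, and they leave both the standard-error method and the fallback trigger open. The rule that an average of at least one "exercise session per week will be eligible to continue on to Aim 2" is a continuation criterion and says nothing about the expected spread. The recommendation does not need a value of phi, because the alternative holds about 5% on both sides of 1. This is a cheap improvement.

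**What to change.** In Data analyses, state that Aim 1 will use a log-link Poisson model with one variance method named in advance, either Pearson-scaled (quasi-Poisson) or robust (HC1) standard errors, with a t reference. Either is acceptable: Pearson-scaled errors were slightly nearer 5% unadjusted and HC1 slightly nearer in one assumed adjusted setting, which is too little to rank them. Report the adjusted rate ratio with that interval and the estimated Pearson dispersion. Keep the residual-normality check for the linear models and do not use it to choose the Aim 1 test.

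The cost is one sentence in the plan. If counts are overdispersed, intervals widen by about sqrt(phi): 1.4 times at phi 2, 2.0 at phi 4, 2.8 at phi 8. If phi is below 1 they narrow. If counts are Poisson, the critical value moves from 1.96 to 1.99, which is negligible.

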Aim 2: To determine whether financial incentives will increase the duration of exercise performed by American Indian youth at a community fitness center. Participants who complete Aim 1 will be re-randomized to one of two groups for a second 16-week period of exercise: Control (\$4/session, up to 3 sessions/week), or Incentive (\$4, \$7, or \$10 for 20-, 40-, or 60- minute sessions, respectively, up to 3 sessions and \$30/week). Transportation and professional supervision will remain the same as in Aim 1. A secondary goal is to assess the association between exercise duration and changes in diabetes-related risk factors.

Aim 3: To determine whether ongoing incentives are required for maintenance of fitness center utilization established with financial incentives. Participants who complete Aim 2 will enter a third 16-week exercise period with diminished monetary incentives. Each person will be re-randomized to one of two incentive structures: a) Ramp-down, with financial incentives diminishing to zero by 8 weeks, or b) Raffle, with monetary prizes awarded through a drawing in which chances of winning are dependent on frequency and duration of exercise. We hypothesize that exercise behavior will remain above zero even after financial incentives decline and that the Raffle approach will reinforce the best exercise behavior maintenance. Clinical diabetes risk outcomes will be measured as in Aims 1 and 2.

Aim 4: To measure the impact of physical activity and physical fitness on circulating biomarkers of metabolic disease risk. Normal weight American Indian youth with either low physical activity and fitness or high physical activity and fitness will be studied on a single occasion. Serum/plasma concentrations of lipids, amino acids, and related markers of inflammation, and oxidative and vascular stress will be compared among the normal weight participants and the overweight/obese youth enrolled in Aims 1-3.

This study will clarify how specific incentive structures can be used to promote exercise in a population of adolescents at exceptionally high risk for diabetes and cardiometabolic disease. The study will also provide needed insight on the volume of exercise needed to elicit changes in clinical outcomes. These results will be used to develop better lifestyle intervention strategies for American Indian youth.

[figure not shown]
RESEARCH STRATEGY: APPROACH

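### Aim 2's hypothesis is about time per visit, but its primary outcome is total exercise time, and no comparison of session length or visit count between the Aim 2 arms is specified

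*Combined protocol and SAP*

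**What the plan says.** The Aim 2 part of Incentive programs states the hypothesis that "exercise time per visit will vary with the amount of money offered" for longer sessions, and adds: "The incentive is meant to encourage at least 60 minutes of MVPA per exercise session". Fig 2 pays the Incentive arm $4, $7 or $10 for a 20-, 40- or 60-minute session. The Control arm receives $4 at each length.

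The Exercise training section keeps three measures apart: "Exercise will be quantified by frequency (sessions per week), duration (length of sessions), and total volume". It also leaves both components to the participant: "Each participant will be able to choose the frequency of visits to the wellness center and the length of time engaged in MVPA".

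Data analyses then says that for Aim 2 "a more conventional regression model will analyze the primary outcome, which is the total time that participants engage in exercise". Visit count is named as a primary outcome for Aim 1 only. In Specific Aims, the secondary goal for Aim 2 reads: "A secondary goal is to assess the association between exercise duration and changes in diabetes-related risk factors". That is an association with risk factors, not a comparison of the arms.

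On scope, the Aim 2 title concerns exercise by "American Indian youth at a community fitness center". Data analyses does not repeat that limit. Of extra activity entered in the log book, Exercise training says: "This information will be used as part of the data analysis plan if applicable".

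**The concern.** By the protocol's own definitions, total time is not duration. It mixes session length with attendance, and the Aim 2 payment scheme could move either. A 40- or 60-minute visit pays the Incentive arm more than the Control arm, so the scheme may change how often participants come as well as how long they stay.

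Aim 1 shows the contrast: its hypothesis is about session frequency and its primary outcome is the number of visits, so the two match.

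At stake is what Aim 2 can conclude. A significant difference in total time could be reported as evidence that paying for longer sessions lengthens them when only attendance rose. A null result could hide a real change in session length. No other specified comparison of the arms would show which component moved.

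**Working it through.** **Check of the plan's own Aim 2 figures.** 3 sessions × 16 weeks = 48 sessions. 48 × $4 = $192 (Control) and 48 × $10 = $480 (Incentive). Both agree with the protocol. It gives no power calculation, effect size, expected visit count or expected session length for Aim 2, so there is nothing further to reproduce.

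**Identity.** For fitness-center exercise, total time = number of visits × mean minutes per visit. The session lengths of 40 and 60 minutes below are Fig 2 tiers. The visit counts are chosen for illustration, within the 48 targeted sessions.

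| Case | One arm | Other arm | Total time | Minutes per visit |
|---|---|---|---|---|
| Visits only | 24 × 40 = 960 | 36 × 40 = 1,440 | 1,440/960 = 1.50 (+50%) | 40/40 (no change) |
| Masking | 36 × 40 = 1,440 | 24 × 60 = 1,440 | no difference | 60/40 = 1.50 (+50%) |
| Milder masking | 36 × 40 = 1,440 | 30 × 48 = 1,440 | no difference | 48/40 = 1.20 (+20%) |

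In the masking row, visits fall by one third (24/36 = 0.667).

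**Is masking what the payments would produce?** In the Incentive arm, 36 visits at $7 pay $252 and 24 visits at $10 pay $240. The schedule does not reward trading visits for length, so masking is possible but not predicted.

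**Illustrative simulation.** All inputs are assumed except the arm sizes of 40 and 45, which are half of the 80-90 participants entering the exercise program with no loss; 25 per arm assumes attrition. Visits were gamma-Poisson (shape 4, limited to 1-64, so non-attenders are excluded). Minutes per visit had SD 10, limited to 20-90. Two-sided t-tests at 0.05 were used, with 5,000 runs. Entries are the share of runs significant at 25/40/45 per arm.

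| Scenario over 16 weeks | Total time | Minutes per visit |
|---|---|---|
| Visits only: 1.5 vs 2.25 per week, 40 min | 62% / 84% / 87% | about 5% |
| Length only: 40 vs 50 min, 1.5 per week | 28% / 38% / 42% | 94% / 99% / 99.7% |
| Offsetting: 1.875 × 40 vs 1.5 × 50 | about 5% | 94% / 99% / 99.8% |

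The percentages depend on the assumed spreads. The mismatch itself follows from the identity alone.

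**Is another comparison specified?** The between-group regressions in Data analyses are for the primary outcomes. The sentence on secondary outcomes concerns the effects of exercise training and names neither session length nor visit count.

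**The case against.** The best defence is that total time is a good primary outcome. It is defined for everyone randomised, including participants who never attend. Minutes per visit is undefined at zero visits and conditions on attendance after randomisation. This stands, and it is a reason to keep total time as primary. It does not make total time a test of the stated hypothesis.

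Data analyses also provides for additional group comparisons and unlisted secondary outcomes, which might reach visit count. But the additional comparisons are a screen for confounders, and the secondary outcomes concern training effects. Neither specifies the missing Aim 2 comparisons.

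Total time has no stated unit or window, so a per-session meaning is not strictly excluded. It is not the plain reading, and if it was intended the text still needs correcting. The identity also assumes that exercise elsewhere is not counted, which is why the scope needs settling.

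Two limits are fair. Masking is the weaker half of the argument, because the payment schedule does not favour it. Participants with no visits may be few, because entry to Aim 2 requires an average of at least one session per week in Aim 1.

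Finally, session length and frequency will be recorded, so they could be reported later. They would then be chosen after the fact rather than pre-specified.

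**Conclusion.** The concern holds. The Aim 2 hypothesis is about session length, the primary outcome is total time, and no comparison of the Aim 2 arms on session length or visit count is specified. The randomised comparison of total time is not biased; the fault lies in what may be concluded from it.

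In the illustrations, total time differs by 50% with session length unchanged, or is identical with sessions 50% longer. These sizes rest on chosen visit counts, and the documents give no basis for saying how likely either pattern is. Confidence is high on the mismatch, which needs only the protocol's own definitions. It should be fixed, because an attendance-only effect could otherwise be credited to the session-length hypothesis. The open question of whether log-book exercise counts is a smaller point.

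**What to change.** - In Data analyses, keep total exercise time over the 16-week Aim 2 phase as the primary outcome, and count non-attenders as zero.
- Reword the Aim 2 hypothesis in Incentive programs, and the planned conclusion, to refer to total time.
- Confirm that total time counts fitness-center exercise, as the Aim 2 title implies. Analyse log-book exercise done elsewhere separately.
- Pre-specify two secondary between-arm comparisons for Aim 2: mean moderate-to-vigorous minutes per attended session, and visit count. Use the same minutes measure in the total and per-session outcomes so that the components multiply to the total.
- Report the number of participants with no visits by arm.
- State that no claim about session length will rest on total time alone, and that minutes per session will be read beside visit count because it depends on attendance after randomisation.

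The cost is some wording and two secondary models, using heart-rate recordings and session logs already planned. The downside is that session length becomes a secondary question of Aim 2, and minutes per session stays undefined for anyone with no visits.
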